### Specific Aims

The long-term goal of this research is to improve outcomes for patients with sleep disorders. The overall objective of the current application is to test preliminarily remote monitoring and ecological momentary assessment (EMA) methods for measuring the impact of insomnia treatment on daytime symptoms (i.e., to employ EMA as an outcome measure). Based on prior research, our central hypothesis is that relative to placebo, suvorexant improves daytime insomnia symptoms as assessed via EMA.

Specific Aim 1: To employ ecological momentary assessment (EMA) methods to evaluate the impact of suvorexant on daytime insomnia symptoms among community-dwelling older adults with insomnia.

Hypothesis 1: Relative to placebo, suvorexant improves alert cognition and daytime symptoms as assessed via EMA.

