## **SAMPLE SIZE AND DATA ANALYSIS**

### **Sample Size**

The DISS will serve as our primary endpoint, and the power/sample size analysis is based on this primary endpoint. Our mixed model approach depends on the size of the intra class correlations (ICC) between repeated measures. Based on results from our prior research), with a sample size of 20 completers each arm and 20% attrition rate, we would have the power of 0.92 to detect a medium effect size of Cohen's  $d=0.5$  based on simulation analysis at the  $\alpha$  level of 0.05. Given the measurement sensitivity of our approach, we anticipate sufficient power to detect differences between groups for both cognitive and sleep outcomes.

Multiple corrections will be performed at the critical p-values of 0.05, 0.025, and 0.017 to show minimum and maximum sensitivities using the false discovery (FDR) method, which

is contingent upon the number of outcome measures that exceed these given critical values.

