#### Main Analysis

The Primary Endpoint (PE) is the between-group difference (SUV vs PBO) in each DISS subscale at four EMA time-of-day assessments (Morning, Midday, Afternoon, Evening) across the study period. Based on our current MISP, we anticipate high adherence with >80% completion of all assessments. We will fit linear mixed-effects models for each subscale, including fixed effects for Group, Time of Day, Day (1–16 continuous), age, and sex; and a random intercept for each participant. The Group×Time interaction will be evaluated using a 4-degree-of-freedom Wald test to determine whether suvorexant and placebo differ at any time of day. If needed, the generalized additive model (GAM) will be used to account for the non-linear time effects. Covariates will be limited to age and sex at birth. Multiple imputation will be implemented for missing data; to confirm the assumptions of multiple imputation that data is missing at random, we will perform sensitivity analyses.

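### The only primary test named is an unsigned multi-degree-of-freedom test, so a significant result does not by itself support the hypothesis of improvement

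*Combined protocol and SAP*

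**What the plan says.** The hypothesis in Specific Aims has a direction: "Relative to placebo, suvorexant improves alert cognition and daytime symptoms as assessed via EMA". The central hypothesis in the same section is worded the same way.

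The Main Analysis defines the endpoint without one: "The Primary Endpoint (PE) is the between-group difference (SUV vs PBO) in each DISS subscale at four EMA time-of-day assessments". Each subscale gets its own linear mixed model with "fixed effects for Group, Time of Day, Day (1–16 continuous), age, and sex; and a random intercept for each participant". The test is then specified: "The Group×Time interaction will be evaluated using a 4-degree-of-freedom Wald test", and its purpose is "to determine whether suvorexant and placebo differ at any time of day". Secondary Analyses applies the same approach to fatigue/sleepiness, positive affect and negative affect.

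The Sample Size section names a single standardised effect: "we would have the power of 0.92 to detect a medium effect size of Cohen's" d = 0.5. It does not say whether this is an effect averaged over the day or an effect at one time, and it gives no ICC. The same section describes a false-discovery-rate correction across outcome measures. That correction concerns the number of outcomes, not the direction of an effect.

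No section gives a signed contrast, an overall group effect, a procedure for the individual times of day, or a reading for a result in which the times disagree.

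**The concern.** A two-sided 1-df test comes with one estimate, and the sign of that estimate settles how a rejection is read. A 4-df Wald test comes with four estimates that may point in different directions, and the statistic takes the same value if all four signs are reversed. Benefit, harm and a reshaped day with no net change can all produce a small p-value.

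The imbalance is made worse by the design. Contrasts between times of day are made within persons over many surveys and are precise under the planned model. The average group difference rests on about 40 people and is not. The joint test is therefore much more sensitive to a change in the shape of the day than to an even improvement across it, which is the simplest reading of Hypothesis 1. At stake is whether the trial's main p-value answers the question that the trial asks.

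**Working it through.** **Inputs.** From the documents: 20 completers per arm, alpha 0.05, d = 0.5 (Sample Size); four surveys a day for 16 days (Daily Survey Completion); more than 80% completion expected, and a random intercept (Main Analysis). Assumed: ICC 0.2, 0.3, 0.5 and 0.7; total survey SD of 1; exactly 80% completion; no person-by-time-of-day variance; normal approximation. The patterns of effect are illustrations and do not come from the documents.

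**The plan's own figure.** A plain two-sided comparison of 20 against 20 at d = 0.5 has power 0.35. A 1-df comparison of participant means over 64 surveys, with SD √(ICC + (1−ICC)/64), reaches 0.92 only at an ICC of about 0.21; it gives 0.81 at 0.3 and 0.60 at 0.5. Without the ICC, the stated 0.92 can be neither confirmed nor refuted.

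**Which test.** With Group in the model and four times of day, a pure interaction has 3 df. Four df fits the joint hypothesis that all four time-specific differences are zero, which agrees with the stated purpose. The calculation uses that reading and checks the other below.

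**Formulas.**
- Within-person part of the variance of one time-specific group difference: v = 2(1−ICC)/(20 × 16 × 0.8) = 2(1−ICC)/256.
- Variance of the averaged group difference: V = 2·ICC/20 + v/4.
- Noncentrality for differences d_t with mean d̄: λ = Σ(d_t − d̄)²/v + d̄²/V.
- Power of the joint test: P(χ²₄(λ) > 9.488).
- Chance that the signed average favours suvorexant: P(Z > 1.96 − d̄/√V).

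At ICC 0.5, v = 0.00391 and V = 0.0510. The SE of a contrast between two times is √(2v) = 0.09 SD, against √V = 0.23 SD for the average.

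**Patterns.**
- Crossing (−0.15, −0.15, +0.15, +0.15): λ = 4 × 0.0225/v = 0.09/v.
- Morning only (−0.3, 0, 0, 0): d̄ = −0.075 and Σ(d_t − d̄)² = 0.225² + 3 × 0.075² = 0.0675, so λ = 0.0675/v + 0.005625/V.
- Uniform benefit of 0.5: λ = 0.25/V.

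| ICC | Crossing: λ, power | Morning worse: λ, power | Uniform benefit: λ, power (4 df) | Uniform benefit, signed 1-df average |
|---|---|---|---|---|
| 0.2 | 14.4, 0.88 | 11.1, 0.76 | 11.6, 0.79 | 0.93 |
| 0.3 | 16.5, 0.92 | 12.5, 0.82 | 8.0, 0.60 | 0.81 |
| 0.5 | 23.0, 0.98 | 17.4, 0.93 | 4.9, 0.39 | 0.60 |
| 0.7 | 38.4, >0.99 | 28.9, >0.99 | 3.5, 0.29 | 0.47 |

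A uniform worsening of 0.5 SD has the same 4-df probabilities as the uniform benefit. The signed average counts the crossing pattern as favourable 2.5% of the time and the morning-only worsening about 1% of the time.

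**If the test is the 3-df interaction.** At ICC 0.3 the crossing pattern gives 0.94 and the morning-only worsening 0.85. A uniform benefit is then detected only at the 5% error rate.

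**If people differ in their time-of-day profile.** Suppose a share p of the variance is person-by-time-of-day and the model accounts for it. Then v = 2p/20 + 2(1−ICC−p)/256. At ICC 0.3 with p = 0.05, v = 0.0101 and λ = 8.9 for the crossing pattern, giving 0.66; with p = 0.10, v = 0.0147 and λ = 6.1, giving 0.48. The morning-only figures become 0.53 and 0.38.

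**The case against.** Pairing a directional hypothesis with a non-directional test is ordinary practice and not an error. The endpoint consists of four signed differences, the fitted model will estimate them, and a careful report would show them. The study also calls itself preliminary. All of this stands, and it limits the point to how a significant joint result is to be read.

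Three stronger readings are tempting and are not supported:
- A reader might infer that the trial would declare success on a harmful pattern. The plan states no success rule, so all that can be said is that the named test would be significant.
- A reader might infer that scales scored in opposite directions could cancel. Each subscale has its own model, so they cannot; stating the signs is a small clarification.
- A reader might infer that morning worsening is to be expected. The documents offer nothing on how likely any pattern is, and the figures show only what the test responds to.

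The size is also open to challenge. No ICC is given, and person-by-time variance, if modelled, would cut the crossing and morning-only figures considerably. The planned random-intercept model does not include that variance. Either way, the statistic remains unsigned.

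Finally, time of day is a deliberate part of the endpoint, and letting only the daily average carry a claim would be costly. A 0.5 SD benefit at one time is detected with probability above 0.99 by the joint test, but about 0.1 by the average (0.13 at ICC 0.2, 0.07 at ICC 0.7). That is a good reason to keep the joint test and add to it.

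**Conclusion.** The point holds as a gap between hypothesis and test. Specific Aims claims improvement, the Main Analysis names only an unsigned test, and nothing connects the two. This follows from the text and depends on no assumption.

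The size is conditional on the inputs listed above. Over ICC 0.2 to 0.7, the joint test is significant with probability 0.88 to above 0.99 for a net-zero crossing of 0.15 SD and 0.76 to above 0.99 for a morning-only worsening of 0.3 SD. For a uniform benefit of the size used in the Sample Size section the probability runs from 0.79 down to 0.29, and a signed average from the same model would raise it to between 0.93 and 0.47. Adding the average therefore improves power for an even benefit as well as making the result interpretable. The change should be made before analysis, but the gap does not invalidate the design.

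**What to change.** In the Main Analysis:

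1. Keep the 4-df test, written out as the joint hypothesis that all four time-specific group differences are zero, as the test of any time-of-day difference.
2. Add, from the same model, the group difference averaged over the four times of day (1 df, with 95% CI) as the pre-specified test of overall improvement. State the beneficial sign of each subscale.
3. Report all four time-specific differences with CIs adjusted for the four comparisons. Adjustment matters: with unadjusted intervals, at least one time would appear to favour placebo by chance in about 4–6% of subscales with no true effect.
4. Allow a claim of improvement at a particular time only if the joint test is significant and that time's adjusted CI favours suvorexant. Report any time whose adjusted CI favours placebo beside the overall result.
5. Say how the averaged contrast and the joint test enter the multiplicity procedure in the Sample Size section.

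This takes a few sentences, with the same data and model. The cost is one more pre-specified contrast to carry through the multiplicity procedure, and a benefit confined to one time of day would be reported as time-specific and not as overall improvement.

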### Design

This is a single-site, double-blind, randomized, placebo-controlled clinical trial. The study employs a two-group (suvorexant, 20mg, qhs, versus placebo) parallel design and involves remote (baseline) assessments, 16-day active treatment phase with intensive ambulatory monitoring via wrist actigraphy and ecological momentary assessment (EMA). Outcome

assessments are conducted at two weeks while participants are on study treatment or placebo and include self- report questionnaires and comprehensive cognitive testing administered by computer.

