### **Remote Assessments (Day 0)**

Study staff will schedule a time for participants to complete the remote assessments. These include a semi-structured interview, validated questionnaires (about 45-60 minutes), and computerized neurocognitive tasks (about 15-20 minutes). Participants will complete the remote assessments over one day (90 minutes) or two days (about 45 minutes each day). For participants who prefer to complete the remote assessments over two days, the first day will include the consent and interview. The second day will include the validated questionnaires and neurocognitive tasks.

Participants use a special research smartphone app for this study, which will capture daily surveys (described below). All study tasks will be remote, e.g., over the phone or via secure teleconferencing platforms like Zoom. During the remote assessments, participants will have many breaks to help them stay refreshed. Participants can also request a break after any task.

Neurocognitive tasks are computerized measures that include the psychomotor vigilance test (PVT), Stroop Task, and a Task-switching exercise developed for use among older adults. To help participants complete these tasks, study staff will email or text participants a link, which will enable completion of the computerized tasks on participants' smartphone, laptop, or desktop computer. In the tasks participants will be asked to respond to words, shapes, and colors on their screens.

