### **Daily Survey Completion (Days 1-16)**

While participants wear the actigraph, they will also complete brief surveys on their mobile phones. The surveys are sent to participants 4 times a day for 16 days. Each survey takes less than 2 minutes to complete. Participants' phones will send them notifications for each survey. At the start of the study, participants will choose what time they want surveys to start. Every morning, participants will complete a survey that includes a brief sleep diary and questions about generalized quiet time activities and how they feel. Next, participants will complete three more surveys throughout the day. These surveys also ask about how they feel. These surveys will be given at random times throughout the day, about two hours apart over the next 12 hours. Study staff will be available to answer any questions or give support. Contact information for study staff and technical support will be given to them.

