#### Secondary Analyses

To examine the effects of treatment with each secondary EMA endpoint including fatigue/sleepiness, positive affect, and negative affect, we will employ the model described above (i.e., same approach as used in the primary analysis). To examine the effects of treatment on 1) sleep continuity variables (sleep onset latency, wake after sleep onset, sleep efficiency, and total sleep time) as measured by sleep diary and actigraphy, 2) self-report questionnaires, and 3) cognitive testing, scores will be compared both within and between-groups adjusting for baseline values using analysis of covariance (ANCOVA). This procedure is known to maximize power.

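### The primary and secondary EMA models use no pre-treatment symptom level, which gives up precision that a Day 0 score could recover at almost no cost

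*Combined protocol and SAP*

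**What the plan says.** Main Analysis defines the endpoint: "The Primary Endpoint (PE) is the between-group difference (SUV vs PBO) in each DISS subscale at four EMA time-of-day assessments". The model is described as "including fixed effects for Group, Time of Day, Day (1–16 continuous), age, and sex; and a random intercept for each participant", and the list is then closed: "Covariates will be limited to age and sex at birth". The test is given as "The Group×Time interaction will be evaluated using a 4-degree-of-freedom Wald test", with the stated purpose of finding a difference at any time of day.

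On timing, Design refers to a "16-day active treatment phase with intensive ambulatory monitoring via wrist actigraphy and ecological momentary assessment (EMA"), and Daily Survey Completion (Days 1-16) says "The surveys are sent to participants 4 times a day for 16 days". The Suvorexant section gives 16 nights of pills at bedtime. Of the Day 0 assessments, Remote Assessments (Day 0) says "These include a semi-structured interview, validated questionnaires (about 45-60 minutes), and computerized neurocognitive tasks". It names no questionnaire, and neither a DISS nor an EMA run-in is described there. According to Eligibility/Consenting/Phone Call, these assessments come before randomization.

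Secondary Analyses applies the primary model to the secondary EMA endpoints. Diary and actigraphy sleep variables, questionnaires and cognitive tests are instead analysed "adjusting for baseline values using analysis of covariance (ANCOVA). This procedure is known to maximize power".

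**The concern.** Group is a between-person factor. A random intercept gives the group contrast an honest standard error, but it does not take person-to-person variance out of that error. More surveys per person do not remove it either, because they only average down the within-person part. A covariate that predicts a person's usual symptom level does remove some of it. The plan uses that device for several lesser outcomes, says why, and rules it out without explanation for the endpoint that set the sample size. With 20 completers per arm, what is at stake is the chance of detecting the target effect and the width of the confidence interval around it.

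**Working it through.** **Inputs from the documents.** 20 completers per arm, d = 0.5, alpha 0.05 and stated power 0.92 (Sample Size); 4 surveys a day for 16 days = 64 (Daily Survey Completion); completion above 80%, so 0.8 × 64 ≈ 51 surveys per person (Main Analysis).

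**Assumptions.** A two-sided test; d in units of the single-survey total SD; ICC 0.2 to 0.7; and r, the within-arm correlation of the baseline score with a person's on-treatment mean, 0.2 to 0.7. The documents give none of these.

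**The stated power.** Sample Size says that power depends on the ICC but gives no value, so 0.92 can be neither reproduced nor refuted. A normal approximation with 51 to 64 surveys returns 0.92 at an ICC of 0.205–0.208 (two-sided, 1 df), 0.254–0.257 (one-sided, 1 df) or 0.135–0.139 (4 df, constant effect). The range below therefore starts at 0.2.

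**Where the error comes from.** The variance of a person's mean is v = ICC + (1 − ICC)/51. The standard error of the average group difference is SE = √(2v/20). The share due to stable person differences is ICC/v.

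- ICC 0.2: v = 0.2157, SE = 0.147, share = 93%
- ICC 0.5: v = 0.5098, SE = 0.226, share = 98%
- ICC 0.7: v = 0.7059, SE = 0.266, share = 99%

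**Effect of a baseline covariate.** Adjusted SE = SE × √(1 − r²) × √(1 + 1/36). The last factor is the small price of estimating one more coefficient. Power is from the noncentral t with 36 df unadjusted and 35 df adjusted, for the 1-df average difference:

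| ICC | none | r = 0.2 | r = 0.3 | r = 0.5 | r = 0.7 |
|---|---|---|---|---|---|
| 0.2 | 0.912 | 0.915 | 0.928 | 0.965 | 0.995 |
| 0.5 | 0.577 | 0.582 | 0.605 | 0.689 | 0.845 |
| 0.7 | 0.449 | 0.453 | 0.473 | 0.550 | 0.715 |

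Apart from that small price, adjustment is worth 1/(1 − r²) times the participants: 1.10 at r = 0.3, 1.33 at r = 0.5 and 1.96 at r = 0.7.

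**The planned test.** With four times of day, a pure Group×Time interaction has 3 df and is free of stable person levels. A 4-df test of any difference at any time also contains the overall group difference, so person variance matters there too. For a constant effect the noncentrality is 0.25/[SE² × (1 − r²)], referred to a chi-square with 4 df. At ICC 0.5 it is 4.90 unadjusted (power 0.389), 5.39 at r = 0.3 (0.425), 6.54 at r = 0.5 (0.508) and 9.62 at r = 0.7 (0.697). At ICC 0.2 the unadjusted power is 0.787.

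**Bias check.** In a simulation of 20,000 runs per setting, the unadjusted analysis returned a mean of 0.50 for a true 0.50 (to within 0.001) and a type I error of 0.051.

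**The case against.** The trial is randomized, so the unadjusted comparison is already valid. A reader might infer that a chance imbalance in prior symptom level would be mistaken for a drug effect, or that the primary result is biased. The documents do not support that: the arms are allocated 1:1 at random, and the model's standard error already carries the person variance. This objection stands and confines the point to precision.

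A reader might also infer that the study is badly underpowered. That does not follow. An ICC near 0.2 is compatible with the stated 0.92, and there the loss is minor. A low ICC is not established either, so the range runs from a small loss to a serious one.

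The proxy may be weak. No Day 0 questionnaire is named, and the Lay Summary itself contrasts retrospective questionnaires with EMA. Nothing in the documents supports an r of 0.5 to 0.7 for such a score. This stands: at r = 0.3 and ICC 0.5 the gain is only 0.577 to 0.605. The higher values are more plausible for the DISS itself or for pre-treatment surveys, but that too is an assumption.

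It is also tempting to say that every survey is on treatment. The documents do not settle this. Pills are taken at bedtime and surveys start in the morning, so some Day 1 surveys may precede the first pill. The model nevertheless takes Day 1 as outcome data, so it is not a planned baseline.

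Finally, the contrast with Secondary Analyses is clean only for questionnaires and cognitive tests. Baseline adjustment is also promised there for diary and actigraphy outcomes, yet both are described as collected on Days 1–16 only.

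**Conclusion.** The point holds as a matter of efficiency, not validity. The covariate list excludes any pre-treatment symptom score from the primary and secondary EMA models, while 93% to 99% of the variance of the average group contrast (ICC 0.2 to 0.7, 20 per arm, 51 surveys each) is of the kind that such a score can reduce. The size of the gain rests on an ICC and an r that the documents do not report. It is negligible at r = 0.2 and modest at r = 0.3. At r = 0.5 or more with an ICC of 0.5 or more it is substantial: about 0.10 to 0.27 in power on the 1-df difference. The 4-df test gains as well, from a lower starting power. I am confident that the omission exists and of its direction, and much less so of its magnitude.

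**What to change.** Replace the covariate sentence in Main Analysis with: *Covariates are age, sex at birth and a pre-specified pre-treatment symptom score.* Name the score for each DISS subscale before unblinding: the closest Day 0 questionnaire, or the DISS itself if it is added to the Day 0 battery. Secondary Analyses then carries the same rule to the secondary EMA endpoints, each with its own named score. The cost is one degree of freedom per model and, if the DISS is added, a survey of under 2 minutes.

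Optional: if app training precedes the first dose, treat any surveys completed before the first pill as baseline and not as outcome data. This adds slight participant burden, and the Days 1–16 survey schedule would have to say so.

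State in Secondary Analyses which pre-treatment value the diary and actigraphy outcomes are adjusted for and when it is collected, since none is described. Report the ICC and the test behind the 0.92, so that the likely gain can be judged.
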